2. SCHEDULE OF ACTIVITIES (SOA)

12-Week Double-Blind Treatment Period

Procedure	Screening	Double-Blind Treatment Period					Early Withdrawal
	Visit	2	3	4	5	6	Early Withdrawal
	Day	-2 to -1	1 (Randomization) ¹	14	28	56	84
Visit window		N/A	± 3 days	±3 days	- 4/+3 days	- 4/+3 days	
Informed consent	X						
PGx informed consent	X						
Demography	X						
Medical history (includes COPD history, COPD exacerbation history, substance usage and family history of premature CV disease)	X						
Chest X-Ray (or CT scan)	X						
Past and current medical conditions (including cardiovascular medical history and therapy history)	X						
Register visit in IRT	X	X	X	X	X		
EFFICACY ASSESSMENTS							
Dispense eDiary and initiate training module within		X					
Review eDiary		←=====→					
Collect eDiary							X
EXACT ²		←=====→					
CAT ³		X		X	X	X	X
SGRQ-C ⁴		X		X	X	X	X
COPD exacerbation assessment		X	X	X	X	X	X
Clinic Visit FEV ₁		X ^{5,6}	X ⁵	X ⁵	X ⁵	X ⁵	X

Procedure	Screening	Double-Blind Treatment Period					Early Withdrawal	
	Visit	1	2	3	4	5	6	Early Withdrawal
	Day	-2 to -1	1 (Randomization) ¹	14	28	56	84	
Visit window		N/A	± 3 days	±3 days	- 4/+3 days	- 4/+3 days		
SAFETY ASSESSMENTS								
AE/SAE review		←=====→						
Double-blind study treatment tolerability assessment (within 5 minutes immediately following dosing)		X	X	X	X	X		
Concomitant medication review	X	X	X	X	X	X	X	
Physical exam, including height and weight	X	X	X	X	X	X	X	
Vital signs	X	X ⁷	X ⁷	X ⁷	X ⁷	X ⁷	X	
12-lead ECG	X ⁸		X ^{7,8}			X ^{7,8}	X ⁸	
Laboratory assessments (including hematology and biochemistry)	X ⁹		X ⁷	X ⁷	X ⁷	X ⁷	X	
Hep B and Hep C screen	X ¹⁰							
HIV screen	X ¹⁰							
Serum pregnancy test (only WOCBP)	X							
Urine pregnancy test (only WOCBP)				X ¹¹	X ¹¹	X ¹¹	X ¹¹	
BIOMARKERS/GENETICS/SPUTUM/PHARMACOKINETICS								
Blood sample for biomarker analysis	X ¹²			X ¹²		X ¹²		
Genetic sample		X ^{13,14}						
Spontaneous sputum sample	X ¹⁵				X ¹⁵			
Serial blood samples for PK analysis (selected sites only)			X ^{13,16}	X ^{13,16}				
OTHER								
Review smoking status	X	X	X	X	X	X	X	

Procedure	Screening	Double-Blind Treatment Period					Early Withdrawal	
	Visit	1	2	3	4	5	6	Early Withdrawal
	Day	-2 to -1	1 (Randomization) ¹	14	28	56	84	
Visit window		N/A	± 3 days	±3 days	- 4/+3 days	- 4/+3 days		
Smoking cessation counselling	X	X	X	X	X	X	X	
Health Care Resource Utilization (HCRU) Review		←=====→						
STUDY TREATMENT/RESCUE MEDICATION								
Inhaler and Propeller Sensor training		X ¹⁷						
Randomization		X ¹⁸						
Double-blind study drug administration ¹⁸		←=====→						
Assessment of study treatment compliance			X ¹⁹	X ¹⁹	X ¹⁹	X ¹⁹	X ¹⁹	
Rescue medication use ²⁰		←=====→						

AM=morning; CAT=COPD Assessment Test; CV=cardiovascular; EXACT=EXacerbations of Chronic Pulmonary Disease Tool; FEV₁=forced expiratory volume in one second; HIV=Human Immunodeficiency Virus; IRT=Interactive Response Technology; PGx=pharmacogenetics research; PK=pharmacokinetic; WOCBP=women of child-bearing potential

1. If a participant meets all of the Inclusion Criteria and none of the Exclusion Criteria, it is possible for him/her to complete the Screening Visit and the Randomization Visit on the same day (e.g., outpatient participant who presents with an acute moderate exacerbation of COPD). In this case, the following assessments/procedures only need to be conducted once: concomitant medication assessment, physical exam, vital signs (including height and weight), and review of smoking status and smoking cessation counselling.
2. Subjects should complete the EXACT as follows: Visit 2: Completed during the Visit (prior to completing other study assessments/procedures); thereafter: completed daily in the evening
3. Subjects should complete the CAT at the visits noted as well as 7 days post EXACT-defined day of recovery after index exacerbation (for the latter, the CAT will be triggered to appear in the e-Dairy on the evening following confirmation of recovery from an EXACT-defined event); the CAT will be completed prior to the SGRQ-C and other study assessments/procedures
4. Subjects should complete the SGRQ-C after completing the CAT and prior to other study assessments/ procedures
5. Spirometry will be performed in the morning (i.e., initiated between 6:00AM and 12:00PM) prior to the first dose of double-blind study treatment (Day 1)/ pre-dose at trough (approximately 24 hours following the previous morning's dose of double-blind study treatment [all other visits]) at two time points each: pre-bronchodilator and post-bronchodilator (approximately 10 to 30 minutes following treatment with albuterol [salbutamol], administered as either four inhalations via the metered-dose inhaler [MDI] (i.e., 400 mcg) with valved-holding chamber or one nebulized treatment)
6. For participants hospitalized for the index exacerbation at Screening, spirometry (as noted in the bullet above) should also be performed in the morning on the day of discharge
7. Pre-dose
8. Single assessment

9. Screening: Due to the short screening window, local laboratory results will be used for purposes of determining subject eligibility for randomization. If local laboratory results are already available within 48 hours from diagnosis of the index COPD exacerbation, these results can be used for determination of subject eligibility; there is no need to take another sample for local analysis. A sample for central laboratory analysis should also be obtained.
10. Presence of hepatitis B surface antigen (HBsAg) and/or positive hepatitis C antibody test result at Screening or within 3 months prior to first dose of study treatment or positive test for HIV antibody is exclusionary. NOTE: Participants with positive Hepatitis C antibody due to prior resolved disease can be enrolled, only if a confirmatory negative Hepatitis C RNA test is obtained. Positive hepatitis C RNA test result at Screening or within 3 months prior to first dose of study treatment is exclusionary. NOTE: Hepatitis C RNA test is optional and participants with negative Hepatitis C antibody test are not required to also undergo Hepatitis C RNA testing. Because of the short window for Screening, double-blind study treatment may start before the results of the hepatitis and HIV tests have been received. If subsequently the test(s) is(are) found to be positive, the participant will need to be withdrawn from study treatment and may also be withdrawn from the study as judged by the Principal Investigator in consultation with the Medical Monitor.
11. If the urine pregnancy text result is positive, a blood sample for serum pregnancy testing will need to be conducted to confirm pregnancy status
12. Approximately 20 mL (4 teaspoons) of blood will be collected in all participants at each time point noted; at Screening, the sample should be collected as soon as possible after the participant has completed the informed consent and PRO assessments
13. Informed consent for optional sub-studies (e.g. genetics research, PK) must be obtained before collecting a sample/performing procedure
14. Collected at Visit 2 or any time post-randomization if unable to collect at Visit 2
15. A spontaneous sputum sample will be collected at Screening/Day 1 (pre-dose) and Day 56 in participants who are willing and able to spontaneously produce sputum
16. PK Subgroup: Subset of participants (approximately 300) at selected sites – blood samples will be collected on site at Visit 3 (Day 14) and Visit 4 (Day 28) at trough (pre-test), between 0-1 hour post-dose and between >1 hour to 6 hours post-dose (total of 3 samples at each visit).
17. Inhaler and Propeller Sensor training conducted by reviewing the Patient Information Leaflet and Propeller Sensor Instructions for Use Guide, respectively, with the participant. Additional training may be conducted at the discretion of the Investigator.
18. Day 1: Randomization and the first dose of double-blind study treatment administration (Visit 2/Day 1) should take place in the morning, as soon as possible following determination of eligibility and completion of the baseline PRO measures, including the EXACT-PRO questionnaire for the day of randomization, and FEV₁ measurement and no later than **24** hours after completing these assessments.
19. Daily recording via the clip-on Propeller Sensor for ELLIPTA and in the eCRF via review of the dose counter at Visits 3-6 (for countries where the Propeller Sensor for ELLIPTA is available) or in the eCRF only via review of the dose counter at Visits 3-6 (for countries where the Propeller Sensor for ELLIPTA is not available)
20. Daily recording via the clip-on Propeller Sensor for MDI and via the eDiary (for countries where the Propeller Sensor for MDI is available) or via the eDiary (for countries where the Propeller Sensor for MDI is not available or if nebulized albuterol [salbutamol] is used)

SoA: 12-Week Post-Treatment Follow-Up Period

Procedure	Post-Treatment Follow-Up Period				
	Visit	7	8	9	Early Withdrawal
	Day	Study Day 112 ¹⁰ (Day 28 of the Follow-Up Period)	Study Day 140 ¹⁰ (Day 56 of the Follow-Up Period)	Study Day 168 ¹⁰ (Day 84 of the Follow-Up Period)	
	Visit window	- 4/+3 days	- 4/+3 days	- 4/+3 days	
EFFICACY ASSESSMENTS					
Review eDiary	←=====→				
Collect eDiary			X	X	
EXACT ¹	←=====→				
CAT ²	X		X	X	
SGRQ-C ³	X		X	X	
Clinic Visit FEV ₁ ⁴	X	X	X	X	
Rescue medication use ⁵	X				
SAFETY ASSESSMENTS					
AE/SAE review	X	X	X	X	
Concomitant medication review	X	X	X	X	
COPD Exacerbation Assessment	X	X	X	X	
Physical exam	X			X	
Vital signs ⁶	X			X ⁸	
12-lead ECG ^{6,7}	X			X ⁸	
Laboratory assessments (including hematology and biochemistry) ⁶	X			X ⁸	
Urine pregnancy test (only WOCBP)	X ⁹			X ⁸	

Procedure	Post-Treatment Follow-Up Period				
	Visit	7	8	9	Early Withdrawal
	Day	Study Day 112 ¹⁰ (Day 28 of the Follow-Up Period)	Study Day 140 ¹⁰ (Day 56 of the Follow-Up Period)	Study Day 168 ¹⁰ (Day 84 of the Follow-Up Period)	
	Visit window	- 4/+3 days	- 4/+3 days	- 4/+3 days	
OTHER					
Review smoking status	X	X	X	X	
Smoking cessation counselling	X	X	X	X	
Health Care Resource Utilization (HCRU) Review	< =====>				

CAT=COPD Assessment Test; EXACT=EXAcerbations of Chronic Pulmonary Disease Tool; FEV₁=forced expiratory volume in one second; IRT=Interactive Response Technology; WOCBP=women of child-bearing potential

1. Completed daily in the evening
2. Subjects should complete the CAT at the visits noted as well as 7 days post EXACT-defined day of recovery after exacerbation; the CAT will be completed prior to the SGRQ-C and other study assessments/procedures
3. Subjects should complete the SGRQ-C after completing the CAT and prior to other study assessments/procedures
4. Performed prior to dosing of concurrent COPD treatment(s) and pre-bronchodilator and post-bronchodilator (approximately 10 to 30 minutes following treatment with albuterol [salbutamol], administered as either four inhalations via the metered-dose inhaler [MDI] (i.e., 400 mcg) with valved-holding chamber or one nebulized treatment)
5. Daily recording via the clip-on Propeller Sensor for MDI and via the eDiary (for countries where the Propeller Sensor for MDI is available) or via the eDiary only (for countries where the Propeller Sensor for MDI is not available or if nebulized albuterol [salbutamol] is used)
6. Prior to dosing of concurrent COPD medication(s)
7. Single assessment
8. Procedure completed only if the Early Withdrawal Visit occurs prior to Day 112
9. If the urine pregnancy text result is positive, a blood sample for serum pregnancy testing will need to be conducted to confirm pregnancy status
10. Participants who discontinue from study treatment will move directly into the 12-Week Post Treatment Follow Up Period starting with Visit 7. Visits for these participants will not align to Day 112, 140, 168, rather will occur every 28 weeks following the study treatment discontinuation date.

- The timing and number of planned study assessments, including efficacy (including PRO), safety, PK, biomarkers, health economics or medical resource utilization, or others assessments may be altered during the course of the study based on newly available data (e.g., to obtain data closer to the time of peak plasma concentrations) to ensure appropriate monitoring.
- Any changes in the timing or addition of time points for any planned study assessments, along with any changes to the randomisation including the possible addition of the 25mcg dose strength, must be documented and approved by the relevant study team member and then archived in the sponsor and site study files, but will not constitute a protocol amendment. The IRB/IEC will be informed of any safety issues that require alteration of the safety monitoring scheme or amendment of the ICF.

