Participants will be permitted to continue taking inhaled maintenance COPD medications (e.g., long-acting bronchodilators, long-acting beta₂-agonist/corticosteroid combinations, long-acting muscarinic antagonist/long-acting bronchodilator combinations, etc.). Study-supplied rescue medication (albuterol [salbutamol] metered-dose inhaler [MDI] or nebulas) for treatment of acute symptoms of COPD will also be permitted. Other concomitant medications, may be allowed at the discretion of the GSK Medical Monitor and/or Investigator

Participants will then dose at home each morning until Day 84 (– 4 / + 3 days), with the exception of the days when participants come to the clinic. On those days, they will dose at the clinic.

During the 12-week Treatment Period, participants will return to the clinic on an outpatient basis for Visits 3-6 on Study Days 14 (± 3 day), 28 (± 3 days), 56 (– 4 / + 3 days) and 84 (– 4 / + 3 days) to complete the assessments described in the Schedule of Assessments.

Participants who withdraw from the study before completing the 12-week Treatment Period will be asked to return to the clinic within 24 hours (or as soon as possible) for end of treatment assessments (Early Withdrawal Visit).

If a participant is withdrawn from study treatment, he/she will continue existing maintenance COPD therapy or will be prescribed appropriate treatment for COPD and will move directly to the 12-Week Post-Treatment Follow-Up Period for collection of data starting with Visit 7, 28 days after the discontinuation of study treatment.

12-Week Post-Treatment Follow-up Period: The 12-week period following the last dose of double-blind study treatment.

During the 12-week Post-Treatment Follow-Up Period, participants will return to the clinic on an outpatient basis for Visits 7-9 on Study Days 112 (– 4 / + 3 days), 140 (– 4 / + 3 days), and 168 (– 4 / + 3 days) to complete the assessments described in the Schedule of Assessments.

Participants who withdraw from the study before completing the 12-week Post-Treatment Follow-Up Period will be asked to return to the clinic within 24 hours (or as soon as possible) for end of study assessments (Early Withdrawal Visit).

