8.1. Discontinuation of Study Treatment

A participant may be discontinued from study treatment but continue in the study for collection of data (including efficacy and safety data) and to minimize missing data. Participants who discontinue from study treatment will move directly into the 12-Week Post Treatment Follow Up Period starting with Visit 7, 28 days following the discontinuation date.

[figure not shown]
If a higher than expected number of participants prematurely discontinues double-blind study treatment or prematurely discontinues from the study, additional participants may be randomized, at the discretion of the Sponsor.

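### A footnote to the follow-up schedule spaces visits after treatment discontinuation 28 weeks apart, in conflict with its own table headers, the Synopsis, Section 8.1 and the 12-week follow-up period

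*Protocol*

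**What the plan says.** The Protocol describes follow-up after early treatment discontinuation in four places.

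- **Section 2, follow-up Schedule of Activities (SoA), footnote 10.** Participants who stop study treatment "will move directly into the 12-Week Post Treatment Follow Up Period starting with Visit 7". Their visits will not fall on Study Days 112, 140 and 168 but "rather will occur every 28 weeks following the study treatment discontinuation date".
- **Section 2, column headers of the same table.** Visit 7 is "Day 28 of the Follow-Up Period", Visit 8 is "Day 56 of the Follow-Up Period" and Visit 9 is "Day 84 of the Follow-Up Period", each with a window of -4/+3 days. Footnote 10 is attached to all three headers.
- **Synopsis.** Participants withdrawn from treatment go to follow-up "starting with Visit 7, 28 days after the discontinuation of study treatment". The period itself is defined as "The 12-week period following the last dose of double-blind study treatment".
- **Section 8.1.** These participants enter follow-up "starting with Visit 7, 28 days following the discontinuation date".

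Section 5.1 gives total participation as about 170 days. Section 9 makes adherence to the SoA a requirement of study conduct and allows no waivers.

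**The concern.** The footnote gives the interval in weeks, while every other statement that bears on it works in days or fits a day-based spacing. The footnote also contradicts itself, because it sends participants into a 12-week period and then sets a visit interval longer than that period.

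The other text does not fully settle the matter. The Synopsis and Section 8.1 give a time after discontinuation for Visit 7 only. Footnote 10 is the one sentence that explicitly sets the spacing of Visits 8 and 9 for this group, and it tells sites not to use the listed study days. A site that follows the footnote departs from Section 8.1, and a site that follows Section 8.1 departs from the SoA.

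Several things hang on the timing:

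- Visit 7 is the last visit with routinely scheduled laboratory tests, ECG, vital signs and, where applicable, a pregnancy test. Visits 8 and 9 have none of these.
- Clinic FEV1 is measured at Visits 7, 8 and 9, and CAT and SGRQ-C at Visits 7 and 9.
- AE and SAE collection runs until Visit 9 (Section 9.2.1), and exacerbation collection ends when Visit 9 is completed (Section 12.9.4).
- Study-supplied rescue medication and the restriction on rescue anticholinergics both run through Visit 7 (Sections 7.1 and 7.7.2.1).

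Section 8.1 keeps these participants in the study to collect efficacy and safety data and limit missing data. Visits that fall outside the follow-up period work against that aim.

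**Working it through.** The check is calendar arithmetic.

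**Inputs.** Follow-up length: 12 weeks (Synopsis). Scheduled follow-up visits: Study Days 112, 140 and 168, after end of treatment on Day 84 (SoA). Interval in footnote 10: 28 weeks. Time to Visit 7 in the Synopsis and Section 8.1: 28 days. Planned randomized: about 1,250, with an assumed withdrawal rate of about 20% (Sections 5.2 and 10.1).

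**1. Reproduce the plan's own schedule.**
- 12 × 7 = 84 days of follow-up.
- 112 − 84 = 28; 140 − 84 = 56; 168 − 84 = 84.

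These match the column headers, and the third visit closes the 84-day period.

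**2. Put the two intervals side by side.** One interval of 28 weeks is 28 × 7 = 196 days, seven times 28 days.

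| Visit | 28-day spacing: days after stopping | Within 84 days? | 28-week spacing: days after stopping | Within 84 days? |
|---|---|---|---|---|
| 7 | 28 | yes | 196 | no |
| 8 | 56 | yes | 392 | no |
| 9 | 84 | yes | 588 | no |

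At 28-week spacing the first visit comes 196 − 84 = 112 days after the period has ended, far more than a -4/+3 day window could absorb. Even that first visit, counted from discontinuation alone, exceeds the 170 days given for the whole of participation.

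**3. Example: a participant who stops on Study Day 28.**
- 28-day spacing: Study Days 56, 84 and 112.
- 28-week spacing: 28 + 196 = 224; 28 + 392 = 420; 28 + 588 = 616.

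**4. How many participants.** 0.20 × 1,250 = 250 are assumed not to complete the treatment period. Footnote 10 applies only to those who stop treatment and stay in the study. The Protocol does not divide the 250 between that group and those who leave the study, so the affected number is at most about 250 under the planning assumption, and lower if any of them leave.

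**The case against.** The strongest reply is that this looks like a slip in the unit and the same page exposes it. The headers carrying the footnote mark show Days 28, 56 and 84, the footnote names a 12-week period, and the Synopsis and Section 8.1 both say 28 days to Visit 7. A site would have to override all of these to book a visit at 196 days. This stands as an argument that the literal schedule is unlikely to be followed widely. It does not remove the conflict, because the SoA is binding and the footnote alone addresses the Visit 8 and 9 interval for this group.

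A reader might also infer more than the documents support:

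- **That safety monitoring after stopping would lapse.** It would not. Liver stopping events have their own repeat testing (Appendix 7), clinically significant laboratory values are repeated (Section 9.4.4), SAEs and adverse events of special interest are followed to resolution or stabilization (Section 9.2.3), and pneumonia is followed to clinical resolution (Section 8.1.3). Only the routinely scheduled assessments move.
- **That exacerbation data would be lost.** Exacerbations are also identified from eDiary data (Section 9.1.2). Unscheduled health-care contacts are recorded daily and prompt contact with the investigator (Section 9.10).
- **That the main results are at risk.** The follow-up endpoints are exploratory (Section 4). Participants who stop treatment skip the remaining treatment-period visits, including Visit 6, whatever the spacing of Visits 7 to 9.
- **That about 250 participants are affected, mostly stopping for safety reasons.** The 250 is a ceiling, and the Protocol gives no breakdown of reasons for stopping.

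**Conclusion.** The point holds as an internal contradiction in current operative text. Taken literally, footnote 10 puts Visits 7, 8 and 9 at 196, 392 and 588 days after discontinuation. All three lie outside the 84-day follow-up period and beyond the stated length of participation. The consequence is delay to the last scheduled laboratory tests, ECG and vital signs, to the visit-based FEV1, CAT and SGRQ-C, and to the end of AE/SAE collection, for participants who stop treatment but remain in the study.

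This rests on two things: the literal wording of the footnote, and the assumption that some sites would schedule from it. How many sites would do so, and how many participants are involved, cannot be determined from the Protocol. No sample size, power or error-rate figure depends on the point, and the Day 84 primary analysis is untouched. It deserves correction because the schedule is binding and the repair is very cheap; the expected harm is limited.

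**What to change.** Reconcile footnote 10 with the SoA column headers, Section 8.1 and the Synopsis, so that one interval, stated for each of Visits 7, 8 and 9, applies to participants who stop treatment early and fits the stated 12-week follow-up period. The sponsor should confirm which interval is intended; this review does not choose it. It would help to give the timing of Visits 8 and 9 in Section 8.1 as well, since that section now covers only Visit 7. Notify sites of the correction, and check whether any participant has already been scheduled from the footnote.

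The cost is a minor text change and a site memo. No analysis, sample size or data collection form needs to change on this account.

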PI3Kd inhibitors may also provide benefits in preventing infections by common airway bacterial pathogens such as *S. pneumonia* [Fallah, 2011]. In this report PI3Kd is shown to reduce the macrophage-derived cytokines required to mount an effective antibody response to *S. pneumonia* in the elderly. Furthermore, PI3Kd inhibition restores age-associated aberrant neutrophil migration [Sapey, 2014]. Activation of the PI3Kd pathway in critically ill patients has been linked to impairment neutrophil phagocytosis, which could be restored with a PI3Kd selective inhibitor [Morris, 2011]. Finally, PI3Kd activating mutations have recently been identified in groups of primary immunodeficient patients that suffer from viral infections and recurring lung bacterial infections due to mainly *S. pneumonia* and *H. influenza*. This results in progressive pulmonary sepsis and increasing morbidity and mortality [Angulo, 2013; Lucas, 2014].

Nemiralisib is a potent and highly selective inhaled PI3Kd inhibitor being developed as an anti-inflammatory for the treatment of inflammatory airways diseases. Therefore, it has the potential to be a novel therapy in patients with COPD.

This double-blind (Sponsor Open) study is primarily designed to assess the dose response, efficacy and safety of six dose regimens of nemiralisib (12.5, 50, 100, 250, 500, and 750 mcg QD) and placebo in addition to standard of care (SoC) for 12-weeks in participants with COPD who present with a moderate or severe acute exacerbation of COPD. The option to add a dose strength of 25 mcg following the results of an unblinded interim analysis has been included if further characterization of the lower end of the dose response curve is required.

Standard of Care (SOC) for the index exacerbation is defined for this protocol as treatment with oral/systemic corticosteroid(s) (prednisone 40 mg/day or equivalent) for 5 days **and** antibiotic[s] for 7 days; the dose and/or duration of prednisone (40 mg/day or equivalent) and/or the antibiotic can be modified according to the Investigator's/medically qualified designee's judgement or according to local country/institution practice. The start of SoC is defined as the start of either oral/systemic corticosteroids[s] or antibiotic[s] whichever is earliest. In addition, this study includes a 12-week Post-Treatment Follow-up Period to assess the potential benefit of nemiralisib following completion of treatment.

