10.3.5. Interim Analyses

Interim analyses will be performed during the course of the study.

Interim analyses of the primary endpoint of change from baseline in clinic visit FEV_1 at Day 84 will be performed to determine whether or not any adjustments to the randomization ratio across the nemiralisib doses would help optimize the characterization of the dose response profile. Adjustments could include starting randomization to a nemiralisib dose of 25 mcg QD and/or ceasing randomization to an existing dose(s) of nemiralisib and/or modification of the allocation ratios for the existing nemiralisib doses. Change from baseline in clinic visit FEV_1 will be analyzed by fitting a Bayesian E_{max} dose response model, as described in Section 10.3.1. The timing of interim analyses of FEV_1 will be pre-specified in the RAP, prior to any unblinding taking place.

In addition, interim analyses will be used to assess the study for futility, to amend the stratification proportions by index exacerbation severity status (moderate or severe) and

to assess the study endpoint assumptions made prior to the study. The specific details regarding the interim analyses will be documented, prior to any un-blinding taking place, in the RAP. The timing of these analyses will depend upon recruitment and may be performed at the same time as the interim analyses of change from baseline FEV₁.

Additionally, an unblinded interim analysis will be conducted at the end of the 12-week treatment period to inform internal program-related decision making.

All interim analyses will be based on un-blinded data and will be performed by the study statistics and programming team (see Section 7.4). The randomization schedules and unblinded datasets will be stored on internal restricted drives. The GSK study team, with the exception of the statistics and programming team, will not have access to an un-blinded copy of the randomization schedule during the course of the trial.

The full details of the interim analyses will be pre-defined in the RAP.

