12.9.3. Subsequent COPD Exacerbation(s)

After the index exacerbation of COPD at Screening (Visit 1) has resolved, any randomized participant who experiences worsening of COPD for >48 hours should:

- Contact his/her study investigator and/or research coordinator immediately, and report to the study clinic as required
- If the participant is unable to contact his/her study investigator and/or research coordinator, he/she should contact his/her primary care physician (or other health care practitioner as required) and contact their study site as soon as possible
- Continue to complete the eDiary
- If the participant seeks emergent/acute care for worsening respiratory symptoms, he/she should inform the caring Health Care Provider (HCP) to contact the investigator as soon as possible.

Participants with presence of worsening respiratory symptoms will be classified by the Investigator as having:

- A mild/moderate/severe COPD exacerbation and/or pneumonia
- A lower respiratory tract infection (LRTI) [i.e., other than pneumonia]
- Background variability of COPD
- A non-respiratory-related disease
- Other respiratory-related disease

Investigators and site/hospital staff should remain vigilant for the possible development of pneumonia in patients with COPD, as the clinical features of such infections overlap with the symptoms of COPD exacerbations (See Section 12.9.7).

If, based upon these criteria, a participant's symptoms do not fulfil the diagnosis of a COPD exacerbation and/or pneumonia, then the investigator should use his/her clinical judgment to assess the participant's symptoms (including increased volume of sputum production and/or change in the sputum color) for a diagnosis of LRTI (e.g., acute bronchitis), background variability of COPD, a non-respiratory-related disease or other

respiratory-related disease. Investigator judgment should be used in deciding whether to report the signs and symptoms (and/or determined diagnosis) as an AE/SAE in the eCRF.

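### Filing every randomisation change in the site study files gives blinded investigators avoidable, though only suggestive, information about unblinded interim decisions

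*Protocol*

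**What the plan says.** The second closing note of Protocol Section 2 deals in one sentence with two kinds of change. It covers altered or added assessment times, "along with any changes to the randomisation including the possible addition of the 25mcg dose strength, must be documented", and then requires them to be "approved by the relevant study team member and then archived in the sponsor and site study files". It adds that they will not count as a protocol amendment.

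Section 10.3.5 says where randomisation changes come from. Interim analyses of Day 84 FEV1 "will be performed to determine whether or not any adjustments to the randomization ratio across the nemiralisib doses would help optimize the characterization"; the thing to be characterised is the dose-response curve. The possible adjustments are opening 25 mcg, stopping an existing dose and altering ratios. All interim analyses use unblinded data.

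The reason for opening 25 mcg is printed in Section 3.1, where the option "has been included if further characterization of the lower end of the dose response curve is required", and again in Sections 5.5, 7.1 and 7.2. The Synopsis and Section 7.2 name a second source of change: the internal Safety Review Committee's findings can also halt or reallocate arms.

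On containment, Section 10.3.5 states: "The randomization schedules and unblinded datasets will be stored on internal restricted drives". Section 7.4 confines unblinded interim summaries to specified people and lets an investigator break a code only in an emergency or serious medical condition. Section 9.5 and Appendix 2 withhold from sites those drug-concentration and biomarker results that could unblind.

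**The concern.** The trial is sponsor-open, so the investigators are the main party whose blinding protects the judgements made at the site. Those judgements matter most for the key secondary endpoint, the rate of moderate and severe exacerbations over 12 weeks. Section 12.9.3 states: "Participants with presence of worsening respiratory symptoms will be classified by the Investigator as having" an exacerbation, pneumonia, another respiratory infection, background variability or something else. The treatment that the investigator chooses can make an event moderate (Sections 12.9.2 and 12.9.5), and the investigator takes part in setting its resolution date (Section 12.9.4.1).

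A filed change tells these people that an unblinded analysis or review has led to a particular decision about doses. Expectations formed from it could affect how events are called, who is kept on study and who is enrolled after the change compared with before. Such an influence would be hard to detect or correct afterwards.

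**Working it through.** **1. Does the filing rule reach efficacy-driven changes?** Section 2 covers any change to the randomisation and names 25 mcg. Section 10.3.5 lists that same change, with stopped doses and altered ratios, as a possible outcome of the unblinded FEV1 interims. The two passages overlap completely on this point. No section restricts the content of the site record, delays its filing or limits who at the site may read it.

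**2. Do sites need the record?** Treatment is assigned centrally by the IRT (Sections 7.1 and 7.3), so a ratio or a closed arm is not needed to randomise a participant. The optional 25 mcg dose is already named in Section 7.1 and Table 1, so consent can cover it in advance. Changes in assessment times are different, because sites must act on those.

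**3. What could a site read from it?**
- 25 mcg opened: the most telling change, because its trigger is printed. Even so, the trigger does not say whether low doses look active or inactive.
- Dose stopped or ratio changed: compatible with a safety finding, a plateau, a flat curve or a need for more data in one region.

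**4. How much does it say about an individual participant?** The starting point is Table 2. The ratio printed in the text (3:1:1:1:1:3) has six terms for seven arms, so I use the seven-term ratio 3:1:1:1:1:1:3, with sum 11, which reproduces the table:
- placebo and 750 mcg: 1,250 × 3/11 = 340.9 each (table: 340)
- each middle dose: 1,250 × 1/11 = 113.6 (table: 114)
- table total: 2 × 340 + 5 × 114 = 1,250

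The chance that a new participant receives placebo is the placebo weight divided by the sum of weights. The changes below are illustrations, with the remaining weights left as they are:

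| Filed change | Placebo share |
|---|---|
| None | 3/11 = 27.3% |
| 25 mcg added at weight 1 | 3/12 = 25.0% |
| One middle dose closed | 3/10 = 30.0% |
| Two middle doses closed | 3/9 = 33.3% |
| 750 mcg closed | 3/8 = 37.5% |

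If 12.5, 50 and 100 mcg were closed and their three shares moved to higher doses, placebo would stay at 3/11. The share on 250 mcg or more would rise from 5/11 = 45.5% to 8/11 = 72.7%. The site would know more about the dose mix of later participants, but not about any one participant's code.

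**5. Which endpoints are exposed?** The primary endpoint is the highest FEV1 from valid efforts on standardised vendor equipment (Section 9.1.1), which leaves less room for judgement. The exacerbation count is the exposed one, and only for events after a change has been filed.

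**The case against.** The strongest reply is that a record of a changed ratio is not an unblinded schedule, dataset or summary, so Sections 7.4 and 10.3.5 are not contradicted. That stands: this is a gap beside those controls, not a breach of their wording.

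A reader might infer that a closed or opened arm discloses the direction of the interim result. The documents do not support that. Arms may change on safety grounds, and the FEV1 adjustments aim to characterise the curve, not to favour better-performing doses. The site learns a decision and can only guess at its reason.

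A reader might also try to size the bias, either from the cough imbalance in the proof-of-concept study or by assuming some fall in counted exacerbations. Neither measures the effect of the filing rule. Any unblinding through cough exists whether or not anything is filed. The cough rate comes from 1000 mcg by DISKUS in a different formulation and cannot be carried to every active arm here. An assumed fall in events has no source in the documents, and it could not apply to all 340 v 340 participants when only events after a change are affected.

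Finally, sites cannot be kept wholly uninformed. Under Appendix 3 the investigator submits study documents and status reports to the ethics committee, and participants re-consent to the current form. This also stands, and it shapes the remedy.

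**Conclusion.** The point holds in a limited form. Followed as written, Section 2 hands blinded investigators partial information about interim decisions which the rest of the protocol gives them no reason to have, and which can be avoided at little cost. The exposure lies mainly in the investigator-classified exacerbation rate after a filed change. Individual assignments stay masked: in the illustrations the placebo share moves only from 27.3% to between 25.0% and 37.5%. Those shares rest on the seven-term ratio implied by Table 2 and on hypothetical changes. No size of bias can be derived from the documents, and none is claimed. This is a worthwhile correction to the wording, not a defect that undermines the design.

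**What to change.** Split the second closing note of Section 2:

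- Changes to assessment timing continue to be archived in the site file.
- Efficacy-driven changes to allocation ratios or closed arms are documented by the unblinded statistics team and held in restricted sponsor and IRT files until database lock.
- Site files and the consent form carry a standing statement that a participant may receive placebo or any listed dose, including the optional 25 mcg, and that ratios may change.
- Beyond that, sites receive only what consent, supply and ethics-committee obligations require, in neutral wording that gives no reason for the change.
- Changes made for safety are still communicated to sites.

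The design, sample size and analysis are unaffected. There are two costs. Sites can no longer state the current allocation ratio. A notification route to ethics committees must also be defined that does not pass the efficacy-driven detail through the blinded investigator.
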